4.1.12 Per Protocol Subjects

Per Protocol (PP) Subjects are all Subjects without major protocol deviations that would affect the completeness, accuracy and reliability of the study data. Major protocol deviations¹ that exclude subjects from the PP Population are the following:

- Failure to meet any of the following study entry criteria:
 - Arrhythmia different than PAF (Inclusion Criterion 1)
 - Prior cardiovascular procedures, implants or conditions (Exclusion Criteria 3, 4)
 - Medical conditions (Exclusion Criterion 11)
- Failure to receive the randomized ablation treatment for PVI as specified in Protocol Section 5.2 and Protocol Section 5.3.
- Receipt of a prohibited study drug (amiodarone)
- In addition, the data of Severe COVID-19 Subjects will be censored beginning on the Onset Date of infection.

4.2 Pre-Specification for Analysis

Unless otherwise specified for specific endpoints, the principal analysis population for the effectiveness endpoints is the MITT Population, with treatment groups defined by randomization assignment. Analyses in the PP population will also be conducted as sensitivity analyses.

Unless otherwise specified for specific endpoints, the principal analysis population for the safety endpoints is the Safety Population, with treatment groups defined by randomization assignment. Analyses in the PP population will also be conducted as sensitivity analyses.

¹ Major protocol deviations also include such events as failure of informed consent, confidentiality violations and actions that may affect the subject's rights, safety or well-being. These, while serious, generally do not impact the validity of data collected and so are not part of the per protocol exclusions for outcome assessment.

5 Definition of Study Outcomes

Some study definitions are included here for convenience and are derived from the study protocol. Any discrepancy is inadvertent unless specifically identified as a deliberate change or clarification of the protocol's definition.

5.1 Primary Effectiveness Endpoint (Protocol Section 7.4)

The primary effectiveness endpoint is Treatment Success, which is a composite of the following criteria:

1. Acute Procedural Success AND
2. Chronic Success, defined as freedom from:
 - a. At the Index/Rescheduled Index Procedure: The use of a non-randomized treatment modality for PVI
 - b. After the Blanking Period:
 - i. The occurrence of any Detectable AF, AFL or AT (Section 6.3.10) (excluding CTI-dependent flutter confirmed by EP study)
 - ii. Any cardioversion for AF, AFL or AT (excluding for CTI-dependent flutter)
 - iii. The use of any Type I or Type III anti-arrhythmic medication for the treatment of AF, AFL or AT
 - c. At any time:
 - iv. Re-ablation for AF/AFL/AT (other than for CTI-dependent flutter)
 - v. Use of amiodarone

Endpoint status will be assessed through 360 ± 30 days.

5.2 Secondary Effectiveness Endpoint (Protocol Section 7.5)

The secondary effectiveness endpoint is the same as the primary effectiveness endpoint but will be tested for superiority rather than non-inferiority. The proportion of Pulsed Field Subjects with Treatment Success will be assessed for superiority to the proportion of Thermal Subjects with Treatment Success.

5.3 Additional Effectiveness Endpoints (Protocol Section 7.6)

1. Acute Procedural Success
2. Acute Vein Success
3. Chronic Success
4. Chronic Success Allowing Re-ablation
5. Chronic Success Allowing AADs
6. Treatment Success Allowing Re-ablation
7. Treatment Success Allowing AADs
8. Treatment Success with PVI/CTI only
9. Early Recurrence of AF
10. Rate of Re-ablation
11. PVI Durability at Re-ablation
12. CTI Ablation Failure
13. Control RF Ablation / Cryoablation Effectiveness Comparison
14. AF Symptom Assessment
15. Learning Curve Effectiveness Assessment

5.4 Primary Safety Endpoint

The Primary Safety Endpoint for this study is the Composite Safety Endpoint (CSE) defined in the Protocol as the proportion of Safety Subjects with one or more of the following device- or procedure-related serious adverse events (SAEs) as adjudicated by the Clinical Events Committee (CEC).

Early onset: within 7 days of the Index / Rescheduled Index procedure

- Death
- Myocardial infarction
- Persistent phrenic nerve palsy
- Stroke
- Transient ischemic attack
- Peripheral or organ thromboembolism
- Cardiac tamponade / perforation
- Pericarditis
- Pulmonary edema
- Vascular access complications
- Heart block
- Gastric motility/pyloric spasm disorders

Late onset: any time through the completion of the 12-month assessment

- Pulmonary vein stenosis
- Atrio-esophageal fistula

5.5 Secondary Safety Endpoints

The secondary safety endpoint is Aggregate PV Cross-Sectional Area (Protocol Section 7.2): The paired comparison of change in the computed aggregate PV cross-sectional area between baseline and 3 months between treatment groups.

5.6 Additional Safety Endpoints

1. Severe Ablation Complications (Protocol Section 7.3.1): The proportion of subjects in each treatment group with one or more of the following CSE components (as defined in Protocol Section 7.1, Table 4) will be compared between treatment groups.
 - a. PV stenosis
 - b. Persistent phrenic nerve palsy
 - c. Atrio-esophageal fistula
2. Nonserious / Serious CSEs (Protocol Section 7.3)
3. Post-Blanking Cardioversions (Protocol Section 7.3)
4. Post-Blanking Arrhythmia Hospitalizations (Protocol Section 7.3)
5. Any Related SAE (Protocol Section 7.3)
6. Any Related Stroke or TIA (Protocol Section 7.3)
7. Categorized PV Dimensional Changes (Protocol Section 7.3)
8. Control RF Ablation / Cryoablation Safety Assessment (Protocol Section 7.3)
9. Learning Curve Safety Assessment (Protocol Section 7.3)

6 Multiplicity

The study will be considered successful only if non-inferiority is established at the final analysis for the primary effectiveness endpoint and for the primary safety endpoint. Two secondary superiority tests are also formally pre-specified: (1) Aggregate PV Cross-Sectional Area, and (2) superiority using the primary effectiveness metric of Treatment Success. These will be tested in the above order, each at the 0.025 significance level (one-sided); the hypothesis for superiority of Treatment Success will not be formally tested unless the endpoint of Aggregate PV Cross-Sectional Area has demonstrated statistical significance. Neither secondary test will be conducted if the primary non-inferiority tests for effectiveness and safety do not establish non-inferiority.

7 Comparability Analyses of the Patient Populations

These analyses are intended to determine the similarity of treatment groups and study sites with respect to important demographic or other variables, either known or suspected to have an influence on the outcome variables. The absence of similarity for any baseline variable will identify that variable as a potential covariate in subsequent safety and effectiveness sensitivity analyses. The data for each baseline variable will be presented descriptively. For quantitative variables like age, the mean, standard deviation (SD), median, minimum, and maximum will be presented. For qualitative variables like gender, the number with the characteristic, the total number evaluated, and the percentage will be presented.

7.1 Comparability between Treatments

The comparison of baseline characteristics across treatment groups will apply the following methods. Continuous variables such as age will be compared with two-sided $\alpha=0.05$ Wilcoxon rank sum test or two-sample t-test, and qualitative variables will be analyzed with χ^2 tests, Fisher's exact test or Fisher-Freeman-Halton test. Any important variable found to significantly differ across treatment groups will be considered as a possible covariate in subsequent multivariate safety or effectiveness analyses.

Comparability will be assessed with frequentist statistical tests, but the primary analysis of study results uses Bayesian statistical methods. Tables of baseline demographics or clinical variables in the clinical study report will be summarized using descriptive statistics. Where appropriate, inferential summaries that are consistent with Bayesian methods (such as 95% Bayesian credible intervals) will be presented. The methods used for these summaries are presented in Section 19.

7.2 Comparability between Study Sites

An analysis of comparability across study sites without regard to treatment assignment will be carried out on the same baseline characteristics by the analysis methods described above. Study site differences do not disallow pooling, and in fact the possibility of site-to-site differences is the prime motivator for stratifying the randomization by site. However, variables including study site and the variable found different may be considered as possible covariates in subsequent sensitivity analyses.

8 Patient Accountability and Missing Data

A summary table will provide the total number of subjects enrolled and completed. The subjects eligible for and compliant with each follow-up assessment will be summarized descriptively. Subjects withdrawn will be tabulated with their reasons for withdrawal.

Every effort will be made to collect all data points in the study. The sponsor plans to minimize the amount of missing data by appropriate management of the prospective clinical trial, proper screening of study subjects, and training of participating investigators, monitors and study coordinators. The sponsor will provide a list of subjects who do not complete the trial along with the best information available on why they each left the trial prematurely.

Analyses that are planned for assessing sensitivity of conclusions to missing data are described below in Section 16.

9 Effectiveness Analyses

All effectiveness analyses will be performed in the modified Intent-to-Treat (mITT) population as the principal analyses. Supportive analyses will be conducted in the Per Protocol (PP) population.

9.1 Primary Effectiveness

The analysis of the primary effectiveness endpoint of Treatment Success defined in Protocol Section 7.4 is a test of non-inferiority of the success rate at 12 months. The null and alternative hypotheses are:

$$H_0: P_T \leq P_C - 0.15 \text{ versus } H_A: P_T > P_C - 0.15$$

where P_T is the Treatment Success rate at 12 months in the Treatment Group (Pulsed Field Group), and P_C is the Treatment Success rate at 12 months in the Control Group (RF and cryoablation).

This trial is designed using Bayesian statistical techniques, and the prior distributions for P_T and P_C in these calculations are Beta (0.5, 0.5), which is the Jeffreys non-informative prior. P_T will be determined to be non-inferior to P_C if it can be established that the posterior probability $Pr(H_A | \text{data}) > \Psi_{\text{eff}}$, where $\Psi_{\text{eff}} = 0.956$ is a pre-specified threshold value that controls the one-sided type I error rate (under simulation) at level 0.05. In the absence of missing data, the posterior distributions for P_T and P_C would be conjugate Beta distributions. However, some missing data are expected. Therefore, Bayesian multiple imputation of 12-month outcomes will be employed in the principal analysis. The imputation model accounts for primary outcome information up through the time of censoring. More detail on this imputation is given in Section 13.1.

9.2 Secondary Effectiveness Endpoint Analysis

The secondary effectiveness endpoint is Treatment Success, tested for superiority rather than non-inferiority. The null and alternative hypotheses are:

$$H_0: P_T \leq P_C \text{ versus } H_A: P_T > P_C$$

where P_T is the Treatment Success rate at 12 months in the Treatment Group, and P_C is the Treatment Success rate at 12 months in the Control Group. Modeling will be identical to the test of non-inferiority, and superiority will be concluded if the posterior probability $\text{Pr}(H_A | \text{data}) > \Psi_{\text{eff,sup}}$, where the threshold $\Psi_{\text{eff,sup}} = 0.977$ is a pre-specified threshold value that controls the one-sided type I error rate (under simulation) at level 0.025. In the absence of missing data, the posterior distributions for P_T and P_C would be conjugate Beta distributions. However, some missing data are expected. Therefore, Bayesian multiple imputation of 12-month outcomes will be employed in the principal analysis. The imputation model accounts for primary outcome information up through the time of censoring. More detail on this imputation is given in Section 13.1.

9.3 Additional Effectiveness Endpoint Analyses

9.3.1 Acute Procedural Success

The endpoint is Acute Procedural Success. The proportion of subjects with Acute Procedural Success in each treatment group will be analyzed descriptively: the number with the endpoint, the total number of subjects evaluated, the percentage, and 95% Bayesian credible intervals (BCIs) for the proportion in each group as well as the difference between groups will be presented. The posterior probability that $P_T > P_C$ will be presented. The statistical method will be a Bayesian comparison of proportions as described in Section 19. Exploratory frequentist analyses may also be conducted.

9.3.2 Acute Vein Success per Vein

This endpoint is Acute Vein Success, assessed on a per vein basis. The proportion of veins in each treatment group will be analyzed descriptively: the number with Acute Vein Successes, the total number of veins evaluated, the percentage, and 95% Bayesian credible intervals (BCIs) for the proportion in each group as well as the difference between groups will be presented. The posterior probability that $P_T > P_C$ will be presented. The statistical method will be a Bayesian comparison of proportions as described in Section 19. Exploratory frequentist analyses may also be conducted.

9.3.3 Chronic Success

The endpoint is Chronic Success. The proportion of subjects with Chronic Success in each treatment group will be analyzed descriptively: the number with the endpoint, the total number of subjects evaluated, the percentage, and 95% Bayesian credible intervals (BCIs) for the proportion in each group as well as the difference between groups will be presented. The posterior probability that $P_T > P_C$ will be presented. The statistical methods will be a Bayesian comparison of proportions (with predictions) as described in Section 19. Exploratory frequentist analyses may also be conducted.

9.3.4 Chronic Success Allowing Re-ablation

The endpoint is Chronic Success Allowing Re-ablation. The proportion of subjects with the endpoint in each treatment group will be analyzed descriptively: the number with the endpoint, the total number of subjects evaluated, the percentage, and 95% Bayesian credible intervals (BCIs) for the proportion in each group as well as the difference between groups will be presented. The posterior probability that $P_T > P_C$ will be presented. The statistical methods will be a Bayesian comparison of proportions (with predictions) as described in Section 19. Exploratory frequentist analyses may also be conducted.

9.3.5 Chronic Success Allowing AADs

The endpoint is Chronic Success Allowing AADs. The proportion of subjects with Chronic Success Allowing AADs in each treatment group will be analyzed descriptively: the number with the endpoint, the total number of subjects evaluated, the percentage, and 95% Bayesian credible intervals (BCIs) for the proportion in each group as well as the difference between groups will be presented. The posterior probability that $P_T > P_C$ will be presented. The statistical methods will be a Bayesian comparison of proportions (with predictions) as described in Section 19. Exploratory frequentist analyses may also be conducted.

9.3.6 Treatment Success Allowing Re-ablation

The endpoint is Treatment Success Allowing Re-ablation. The proportion of subjects with the endpoint in each treatment group will be analyzed descriptively: the number with the endpoint, the total number of subjects evaluated, the percentage, and 95% Bayesian credible intervals (BCIs) for the proportion in each group as well as the difference between groups will be presented. The posterior probability that $P_T > P_C$ will be presented. The statistical methods will be a Bayesian comparison of proportions (with predictions) as described in Section 19. Exploratory frequentist analyses may also be conducted.

9.3.7 Treatment Success Allowing AADs

The endpoint is Treatment Success Allowing AADs. The proportion of subjects with Chronic Success Allowing AADs in each treatment group will be analyzed descriptively: the number with the endpoint, the total number of subjects evaluated, the percentage, and 95% Bayesian credible intervals (BCIs) for the proportion in each group as well as the difference between groups will be presented. The posterior probability that $P_T > P_C$ will be presented. The statistical methods will be a Bayesian comparison of proportions (with predictions) as described in Section 19. Exploratory frequentist analyses may also be conducted.

9.3.8 Treatment Success with PVI/CTI Only

The endpoint is Treatment Success with PVI/CTI Only, excluding subjects receiving extra PVI/CTI ablation. The proportion of subjects with Treatment Success with PVI/CTI Only in each treatment group will be analyzed descriptively: the number with the endpoint, the total number of subjects evaluated, the percentage, and 95% Bayesian credible intervals (BCIs) for the proportion in each group as well as the difference between groups will be presented. The posterior probability that $P_T > P_C$ will be presented. The statistical methods will be a Bayesian comparison of proportions (with predictions) as described in Section 19. Exploratory frequentist analyses may also be conducted.

9.3.9 Early Recurrence of AF

The endpoint is Early Recurrence of AF. The proportion of subjects with Early Recurrence of Atrial Fibrillation \leq Day 90 in each treatment group will be analyzed descriptively: the number of subjects with the endpoint, the total number of subjects evaluated, the percentage, and 95% Bayesian credible intervals (BCIs) for the proportion in each group as well as the difference between groups will be presented. The posterior probability that $P_T < P_C$ will be presented. The statistical methods will be a Bayesian comparison of proportions as described in Section 19. Exploratory frequentist analyses may also be conducted.

9.3.10 Re-ablation

The endpoint is Occurrence of Re-ablation. The proportion of subjects with the endpoint through 12 months in each treatment group will be analyzed descriptively: the number of subjects undergoing re-ablation, the number evaluated, the percentage and 95% Bayesian credible intervals (BCIs) for the proportion in each group as well as the difference between groups will be presented. The posterior probability that $P_T < P_C$ will be presented. The statistical methods will be a Bayesian comparison of proportions (with predictions) as described in Section 19. Exploratory frequentist analyses may also be conducted.

9.3.11 PVI Durability at Re-ablation

The endpoint is PVI Durability at Re-ablation, assessed on a per vein basis and also on a per subject basis. For the per-subject analysis, a subject is a “success” if and only if all originally ablated veins have durable isolation. The proportion in each treatment group will be analyzed descriptively: the number with confirmed PVI Durability, the number evaluated, the percentage and 95% Bayesian credible intervals (BCIs) for the proportion in each group as well as the difference between groups will be presented. The posterior probability that $P_T > P_C$ will be presented. The statistical methods will be a Bayesian comparison of proportions as described in Section 19. Exploratory frequentist analyses may also be conducted.

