Secondary safety endpoints, included the rate of all serious adverse events (SAEs) reported at the different follow-up time points, as adjudicated by the CEC, with 7.5% (3/40) of subjects reporting an SAE between index procedure and 30 days (2 AF events, 1 cardiac tamponade), 0.0% (0/40) of subjects reporting an SAE between 30 days and 3 months, 7.5% (3/40) of subjects reporting an SAE between 3 months and 6 months (1 arteriovenous fistula, 2 ATs) and 2.5% (1/40) of subjects reporting an SAE between 6 months and 12 months (1 urinary calculus).

No pulmonary vein stenosis (PVS), esophageal lesions or phrenic nerve impairment was observed in any subject.

The secondary feasibility endpoint was long-term technical success, defined as electrical isolation of the PVs assessed during an electroanatomical mapping procedure performed 3-months following the index procedure, with 41.2% (14/34) of subjects achieving technical success.

For the 40 enrolled subjects, 156 veins were treated at the index procedure, 100% (156/156) were successfully isolated and 70% of ablated PVs remained isolated at the 3-month remapping procedure. Thirty-one (31) of 40 subjects (77.5%) remained free from post-blanking AF, atrial flutter (AFL) or atrial tachycardia (AT) after a mean follow-up of 356 days.

Ten (10) device deficiencies were reported in 8 subjects, none of which were deemed serious or resulted in any associated AEs in subjects. Of the ten deficiencies, one device deficiency was related to a 3rd party guidewire. All procedures were completed as planned and all subjects were successfully treated. All deficiencies were investigated and most resolved with several others under ongoing investigation.

**Conclusion:** These results support the safety and feasibility of the FARAPULSE Pulsed Field Ablation System in the treatment of patients with PAF, with a low rate of primary AEs through 7 days, a high rate (100%) of procedural success and a rate of arrhythmia recurrence consistent with other technologies.

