### **9.2 Randomization**

Subjects meeting all pre-randomization inclusion and exclusion criteria who sign an ICF will be randomized. The study staff will confirm documented inclusion / exclusion success prior to requesting randomization.

Randomization will be achieved by an interactive web-based or phone-based system. Randomization will be stratified by site and use a permuted block design with randomly varying block sizes.

Subjects who meet the inclusion and exclusion criteria will be randomized using a 1:1 allocation ratio.

Each site will utilize only one control modality – either RFA or CBA – and will use that modality for all subjects randomized to the Thermal Group. Site activation and enrollment will be monitored and when necessary controlled to maintain a minimum 40% proportion of Thermal Subjects in either the RFA or CBA modality.

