10.3.7 Categorized PV Dimensional Changes

The endpoint is Categorized PV Dimensional Changes. The distribution of Categorized PV Dimensional Changes between baseline and 3 months in each treatment group will be categorized by treatment group on a per vein basis by maximal % reduction in PV diameters and computed areas into 4 groups: 0-29.9%, 30-49.9%, 50-69.9%, and $\geq 70\%$.

The number of veins with the amount of change by category, the total number evaluated, the percentage, and the results of the Fisher-Freeman-Halton test will be presented.

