19.3 Discrete (Dichotomous) Data: Bayesian Version of a Comparison of Proportions

Given proportions p_t and p_c for a dichotomous outcome, let each be assigned a non-informative Beta(0.5, 0.5) prior. Then the posterior distributions for p_t and p_c follow Beta($0.5+Y_t, 0.5+N_t-Y_t$) and Beta($0.5+Y_c, 0.5+N_c-Y_c$) distributions, respectively, where Y_t and Y_c represent the number of “successes” and N_t and N_c represent the number of “tries” (e.g., subjects) in their respective treatment groups. Credible intervals for p_t and p_c can be individually calculated as the 2.5th and 97.5th percentiles from their respective (beta) posterior distributions. The posterior mean of the difference $p_t - p_c$ is simply the difference in means of the respective beta posterior distributions. The distribution of the difference $p_t - p_c$ can be summarized by any of the following approaches:

Full Monte Carlo Sampling: Drawing a large number of observations (eg., 100,000) from each Beta posterior, and subtracting the sampled values. The posterior probability $P(p_t - p_c < \delta | \text{data})$ is estimated as the proportion of these observations where the difference is less than δ . A 95% equal-tail Bayesian credible interval (BCI) can be calculated from the 2.5th and 97.5th percentiles of the sampled distribution of $p_t - p_c$.

Monte Carlo Sampling and Integration: More precise estimates can be achieved by sampling from only one posterior distribution (say, for p_c). The cumulative distribution function F_{T-C} of the difference $p_t - p_c$ can be written as

$$\begin{aligned} F_{T-C}(\delta) &= P(p_t - p_c < \delta) = P(p_t < p_c + \delta) = \int P(p_t < p_c + \delta | p_c) \times f(p_c) dp_c \\ &= \int F_T(p_c + \delta | p_c) f(p_c) dp_c, \end{aligned}$$

where $f(p_c)$ represents the density of p_c and F_T represents the c.d.f. of p_t .

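### The per-vein analyses in SAP 9.3.11, 9.3.2 and 10.3.7 count veins of one patient as independent, so their intervals, posterior probabilities and p-value are miscalibrated if those veins are correlated

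*SAP*

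**What the plan says.** The unit of randomization is the patient: "Subjects who meet the inclusion and exclusion criteria will be randomized using a 1:1 allocation ratio" (Protocol 9.2).

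Three additional analyses use the vein as the unit.

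- **Durability (SAP 9.3.11):** "PVI Durability at Re-ablation, assessed on a per vein basis and also on a per subject basis". In the per-subject part a patient is a success "if and only if all originally ablated veins have durable isolation". Both parts report 95% credible intervals and the posterior probability that P_T exceeds P_C, from the Section 19 comparison of proportions.
- **Acute vein success (SAP 9.3.2):** the output is "the number with Acute Vein Successes, the total number of veins evaluated, the percentage, and 95% Bayesian credible intervals (BCIs"), from the same method. Protocol 7.6 asks for it over all veins and by vein category.
- **Categorized PV change (SAP 10.3.7):** veins are classified "on a per vein basis by maximal % reduction in PV diameters and computed areas into 4 groups". The output is "The number of veins with the amount of change by category, the total number evaluated, the percentage, and the results of the Fisher-Freeman-Halton test". No credible interval is planned here.

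Section 19.3 gives each arm the posterior Beta(0.5+Y, 0.5+N-Y). It glosses the N tries as "e.g., subjects) in their respective treatment groups" and contains no patient effect. Neither document mentions within-patient correlation. The allowance for exploratory frequentist analyses in 9.3.2 and 9.3.11 specifies no adjustment.

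**The concern.** A patient's veins share an operator, a procedure and an anatomy, so their outcomes need not be independent. Entering veins as N in Section 19.3 gives the posterior the precision of N independent observations. With positive correlation the intervals are too narrow and Pr(P_T > P_C) is too extreme in either direction. With negative correlation the reverse holds. The vein-level Fisher-Freeman-Halton test makes the same assumption, and its p-value is anti-conservative if veins are positively correlated.

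At stake is whether a published 95% interval or posterior probability for durability, a result likely to attract attention for a new energy source, means what its label says.

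**Working it through.** **Pilot inputs (Protocol 1.4.1 to 1.4.3).**

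- IMPULSE: "70% of ablated PVs remained isolated at the 3-month remapping procedure"; 14/34 patients had all veins durable; 156 veins in 40 patients at index, or 3.9 each. The remap vein count is not given, so 3.9 is assumed.
- PEFCAT: 221/243 veins and 46/62 patients. The 243 veins are assumed to belong to the 62 remapped patients, or 3.92 each.
- PEFCAT II: 33/35 veins and 7/9 patients, or 3.89 each.

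The stated percentages reproduce: 14/34 = 41.2%, 221/243 = 90.9%, 46/62 = 74.2%, 33/35 = 94.3%, 7/9 = 77.8%.

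**Step 1: are pilot veins independent?** Under independence the share of patients with all m veins durable is p^m.

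- IMPULSE: 0.70^3.9 = 24.9%, observed 41.2%.
- PEFCAT: 0.909^3.92 = 68.9%, observed 74.2%. Scattering the 22 failed veins at random over 62 patients gives on average 42.7 all-durable patients; 46 or more occurs with probability 0.02.
- PEFCAT II: 0.943^3.89 = 79.5%, observed 77.8%. Nine patients are too few to tell.

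**Step 2: implied ICC.** In a beta-binomial with a = p(1-ICC)/ICC and b = (1-p)(1-ICC)/ICC, the chance that all m veins are durable is B(a+m, b)/B(a, b). Setting this equal to the observed patient rate gives the ICC; the design effect is 1 + (m-1) × ICC.

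- IMPULSE: ICC 0.308; 1 + 2.9 × 0.308 = 1.89.
- PEFCAT: ICC 0.155; 1 + 2.92 × 0.155 = 1.45.

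These are rough: the ranges are 0.10 to 0.52 and 0 to 0.35.

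**Step 3: coverage if the pilot ICCs carry over.** Assumptions: 4 veins per patient, the same ICC in both arms and no true difference. The number re-ablated is not in the documents, so 10, 20, 30 and 50 per arm were taken. Exact coverage of the Section 19.3 interval for the difference:

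- p = 0.70, ICC 0.308: 83.2%, 83.7%, 83.9%, 84.1%.
- p = 0.909, ICC 0.155: 88.5%, 88.8%, 88.8%, 89.3%.
- ICC 0, either p: 94.1% to 95.0%.

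**Step 4: allow for who is re-ablated.** Protocol 4.7.10 and 5.4 require documented Detectable AF, AFL or AT before re-ablation, so patients with every vein durable may be under-represented. In the Step 3 models, the probability of 4 of 4 durable was multiplied by w (the relative re-ablation rate of such patients) and the distribution renormalised. The documents give no value for w. With 20 patients per arm:

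| w | IMPULSE ICC | coverage | PEFCAT ICC | coverage |
|---|---|---|---|---|
| 1 | 0.31 | 84% | 0.16 | 89% |
| 0.2 | 0.13 | 91% | 0.01 | 94% |
| 0.1 | 0.08 | 92% | -0.05 | 97% |
| 0 | 0.02 | 94.5% | -0.18 | 99.5% |

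The figures in Step 3 are thus the no-selection end of a range that runs past nominal.

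**Step 5: acute success.** Every treated vein was isolated in all three pilot studies. If every vein succeeds, with 225 patients per arm (450/2) and 4 veins each, the lower 2.5% limit is 99.7% on 900 veins and 98.9% on 225 patients. Analysis by vein category uses about one vein per patient and is largely unaffected.

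**Step 6: PV change.** The documents give no ICC. With a Dirichlet-multinomial model, category rates based on Protocol Table 1, 225 patients per arm and an assumed ICC of 0.05 to 0.30, the vein-level test rejects a true null about 7% to 26% of the time at nominal 5%. A latent-normal model with 200 per arm, and a chi-square test in its place, gave 8.7% and 12.1% at latent correlations of 0.3 and 0.5. The answer depends on the model and correlation chosen, so these rates are illustrative only.

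**The case against.** The strongest reply is that the direction is not shown for the patients analysed. The pilot remaps were scheduled, and the pilots had a PFA arm only; SAP 9.3.11 covers patients re-ablated after a documented recurrence, in both arms. Step 4 bears this out. A reader might infer that the durability intervals are certain to be too narrow, but the documents do not support that.

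A reader might also turn the coverage loss into a false-positive rate at a posterior probability of 0.975. The SAP sets no threshold for durability: it says only that the probability will be presented. The 0.975 rule belongs to Aggregate PV Cross-Sectional Area (SAP 10.2.1). Nor do all three analyses share one method: 10.3.7 has a p-value and no credible interval.

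Finally, much is already covered. Durability has a per-subject result in the same section, acute success has Acute Procedural Success (9.3.1), and PV narrowing is formally tested per subject (10.2.1). All of this stands and limits the impact. It does not make the per-vein error bars valid: nominal status excuses the absence of a multiplicity adjustment, not a variance that ignores the patient.

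**Conclusion.** The point holds in conditional form and is minor. As written, the vein-level intervals, posterior probabilities and 10.3.7 p-value are calibrated only if veins within a patient are uncorrelated.

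For durability, coverage would be about 83-89% if the pilot ICCs carried over to both arms, and near or above 95% under strong selection against all-durable patients. Neither the ICC nor the selection is known for this trial. For 10.3.7 the p-value is anti-conservative if correlation is positive, by an amount the documents cannot fix. For all-vein acute success the effect is probably small.

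A reader should not infer any threat to the trial's conclusions. These analyses lie outside the testing order in SAP Section 6, and no primary endpoint, formal secondary test or sample-size look uses them.

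**What to change.** Keep the vein counts and percentages as description, and change only the inference.

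- **9.3.11 and all-vein 9.3.2:** take the intervals and Pr(P_T > P_C) from a method that clusters on the patient and allows correlation of either sign. With about 30 or more patients per arm, a Bayesian bootstrap that reweights patients serves: in simulation with the pilot ICCs it covered 93% at 30 per arm and 94-95% at 50.
- **Fewer patients:** the bootstrap covered only 85-93% at 10 to 20 per arm. Use a beta-binomial model with a patient-level ICC, which covered about 95% at the pilot ICCs. State that it is conservative if the correlation is zero (96-98% coverage) or negative, which it cannot represent.
- **No failed vein in an arm:** show counts and the planned per-subject interval (9.3.1, or the per-subject part of 9.3.11).
- **10.3.7:** replace the vein-level p-value with a test on the same table that permutes patients. In simulation it rejected a true null in 3-6% of trials.

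The cost is SAP wording, light programming and possibly wider intervals. Data collection, sample size and formal testing do not change.
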